As part of this pediatric program, a Phase 1 pharmacokinetic (PK) study of tofacitinib in JIA subjects (A3921103) was completed in 2015, and an open-label, non-comparative, long-term extension study (A3921145) is ongoing. Subjects from Study A3921104 were eligible to enter Study A3921145 to continue treatment with tofacitinib 5 mg BID IR tablets or weight equivalent dose of oral solution.

Study A3921104 was designed to provide evidence of efficacy and safety of tofacitinib in subjects with JIA. To limit exposure to placebo in this pediatric population, a randomized withdrawal study design was used. Selection of doses for this first efficacy study of tofacitinib in subjects with JIA was supported by PK data from the completed Phase 1 PK study of tofacitinib in JIA subjects (A3921103) and the benefit/risk profile of tofacitinib in adult patients with RA.

The primary efficacy endpoint of Study A3921104 was met; subjects treated with tofacitinib 5 mg BID had a significantly lower occurrence of disease flare by Week 44 compared to placebo-treated subjects. The type I error controlled (key) secondary endpoints for the study were also met at Week 44. A significantly greater proportion of subjects treated with

Tofacitinib
A3921165

Final Protocol Amendment 8, 01 September 2023

tofacitinib 5 mg BID achieved JIA ACR 50, 30, and 70 responses compared to subjects treated with placebo, and the LS mean change from the double-blind baseline in CHAQ disability index indicated a statistically significant treatment effect favoring tofacitinib over placebo. These results were supported by sensitivity analyses. The proportions of subjects with TEAEs, SAEs, severe TEAEs, dose reductions or temporary discontinuations due to TEAEs were similar between the tofacitinib 5 mg BID and placebo groups during the double-blind phase. A larger proportion of subjects in the placebo group had TEAEs related to the underlying JIA disease than subjects in the tofacitinib 5 mg BID group. A smaller proportion of subjects treated with tofacitinib 5 mg BID discontinued the study because of an AE compared to subjects who received placebo. Disease progression and JIA were the most frequent AEs leading to study discontinuation.

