9.3. Definition of an Adverse Event

An AE is any untoward medical occurrence in a clinical investigation subject administered a product or medical device; the event need not necessarily have a causal relationship with the treatment or usage. Examples of AEs include but are not limited to:

- Abnormal test findings;
- Clinically significant symptoms and signs;
- Changes in physical examination findings;
- Hypersensitivity;
- Progression/worsening of underlying disease;
- Drug abuse;
- Drug dependency.

Additionally, they may include the signs or symptoms resulting from:

- Drug overdose;
- Drug withdrawal;

- Drug misuse;
- Drug interactions;
- Extravasation;
- Exposure during pregnancy (EDP);
- Exposure via breastfeeding;
- Medication error;
- Occupational exposure.

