9.7. Serious Adverse Events

A serious adverse event is any untoward medical occurrence at any dose that:

- Results in death;

- Is life-threatening (immediate risk of death);
- Requires inpatient hospitalization or prolongation of existing hospitalization;
- Results in persistent or significant disability/incapacity (substantial disruption of the ability to conduct normal life functions);
- Results in congenital anomaly/birth defect.

Medical and scientific judgment is exercised in determining whether an event is an important medical event. An important medical event may not be immediately life-threatening and/or result in death or hospitalization. However, if it is determined that the event may jeopardize the subject or may require intervention to prevent one of the other AE outcomes, the important medical event should be reported as serious.

Examples of such events are intensive treatment in an emergency room or at home for allergic bronchospasm; blood dyscrasias or convulsions that do not result in hospitalization; or development of drug dependency or drug abuse.

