### 6.6.1. Adverse Events

Adverse events will be summarized according to Pfizer standards. AE's will be summarized by the separate phases: Part 1, Part 2 of the open-label, and double-blind.

An adverse event will be considered a treatment-emergent AE (TEAE) if the event starts during the treatment phase of interest. In all these analyses, all AEs (ie, an infinite lag) will be counted within each study phase, with the reception of the incidence rate (IR) calculation

for events of interest, where the risk period will be up to 28 days within the last investigational product dose, as defined below.

Selected AEs in double-blind phase will be analyzed using incidence rate (IR) and 95% CI and hazard ratio (HR) and 95% CI using a Cox model, including any TEAE, SAE, adjudicated MAS, serious infections (SI) including tuberculosis, varicella and herpes zoster (HZ) and adjudicated opportunistic infections (OI), adjudicated malignancies, adjudicated GI perforations, and adjudicated CV events.

The IR (expressed in unique number of subjects with events per 100 subject-years) for double-blind phase will be defined as the number of subjects with at least one event during the risk period divided by the sum of the durations of exposures for the subjects during the risk period.

The risk period (RP) for the double-blind phase for each subject will span from day of randomization to the earliest of last contact date and last investigational product dose date + 28 days. The last contact date will be the maximum of: AE start date, AE stop date, last study visit date, withdrawal from study date and telephone contact date. If a subject dies, last contact date will be the death date. First events will be counted within the risk period. If a subject did not have an event or had an event but outside the risk period, the subject will be censored at the end of risk period.

$$\text{IR for DB} = (\text{\#of subjects with first events during the DB risk period}) / (\text{sum of durations of subject exposure during the risk period})$$

The numerator of the IR will include subjects counted only once as soon as they experience a first event during their individual risk period defined above.

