### 7.1. Centralized Coordinating Center (CCC)

This study will utilize a CCC to review and confirm, in real time, efficacy assessments, including sJIA fever assessment, JIA core set variables, extra-articular sJIA features, Adapted JIA ACR response, sJIA disease flare and inactive disease, according to validated criteria, at various time points throughout the study.

In addition, the CCC will review corticosteroid (CS) regimens of study participants. The CCC will suggest a customized 4-week CS tapering schedule for each subject entering Part 2. Subjects are required to contact the investigator if they experience any symptoms of a sJIA flare; if required, an extra unscheduled visit will be conducted to assess the adverse event. The tapering schedule will be re-evaluated in consultation with the CCC.

The CCC will also provide recommendations in case participants are not able to maintain a stable CS dose in the double-blind phase. Furthermore, the CCC will provide guidance regarding discontinuation of any subject based on CS regimen.

For data analysis Pfizer will calculate all the efficacy endpoints in-house, except for double-blind flare, which will be obtained from the CCC's real-time assessments mentioned above.

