### **Appendix 3.12. Investigational Product Discontinuation due to Disease Flare**

To look for subjects who discontinue investigational product due to disease flare, the following CRF forms should be checked:

1. “End of treatment (EOT) double-blind period” form: “Subject Status” question checked as “withdrawn during double-blind treatment period”; “Reason for discontinuation of treatment” question checked as “withdrawn due to insufficient clinical response”
2. “Adverse Event” form: Confirm an adverse event of “sJIA Flare” was recorded on the Adverse Event CRF
3. “Pediatric ACR Response and Disease Flare” form at the Early Termination visit: “Flare Status” checked as “Flare”

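### The double-blind any-TEAE rate and hazard ratio count sJIA flares as adverse events and so mix loss of efficacy with drug safety; the SAE versions do so only as far as flares are serious

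*SAP*

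**What the plan says.** Four statements matter together.

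- **What counts as an adverse event.** Protocol 9.3 lists "Progression/worsening of underlying disease" among its examples and makes no exception for sJIA. Both documents treat flare symptoms this way in conduct; SAP 7.1 says that "an extra unscheduled visit will be conducted to assess the adverse event".
- **How flares reach the adverse event data.** A confirmed double-blind flare leads to discontinuation. To identify those subjects, SAP Appendix 3.12 says: "Confirm an adverse event of “sJIA Flare” was recorded on the Adverse Event CRF".
- **What is analysed.** SAP 6.6.1 says: "An adverse event will be considered a treatment-emergent AE (TEAE) if the event starts during the treatment phase of interest". It then plans incidence rates and a "hazard ratio (HR) and 95% CI using a Cox model, including any TEAE, SAE, adjudicated MAS" and several named event types. First events count, from randomization to the earlier of last contact and "last investigational product dose date + 28 days", so the flare itself falls inside the risk period.
- **What makes an event serious.** One Protocol 9.7 criterion is "Requires inpatient hospitalization or prolongation of existing hospitalization". The Protocol 9.8 exemption for admission with a preexisting condition does not cover a worsening of that condition.

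Neither document excludes flare or disease terms from these analyses or plans a version without them.

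**The concern.** The design withdraws active drug and expects flares to follow in the placebo arm. If those flares are recorded as adverse events, time to first TEAE is partly the primary endpoint again. A flare that comes first also ends that subject's contribution to the any-TEAE analysis, so a later unrelated event is not counted.

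Safety and tolerability are a stated objective, and the open-label phase has no comparator. The double-blind phase is therefore this trial's only controlled safety comparison. Its two broadest summaries, any TEAE and SAE, could look neutral or favourable because the drug works, and an excess of other adverse events could be understated in them.

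**Working it through.** **Inputs from the documents.** Flare hazard ratio 0.36, placebo median time to flare 236 days, 28 flares at the First Analysis and 37 at the Final Analysis, one-sided 2.5%, 1:1 allocation (all SAP 5.1).

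**Inputs not in the documents (assumed, shown as ranges).** The rate of a first non-flare adverse event on placebo, the rate of non-flare SAEs, and the share of flares that are serious.

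**1. The plan's own figure.** A two-look calculation with gamma-family spending at 28 and 37 flares gives efficacy z of -1.973 and -2.586 and power of 80.4% with the futility rule applied. These match SAP Table 2. The futility z comes out at -1.251 against the stated -1.240, which does not matter here. This confirms how 0.36 is used; the 236-day median does not enter that calculation and is taken as given.

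**2. Flare rates.** With exponential times, the placebo hazard is ln 2 / 236 = 0.002937 per day. Multiplied by 365.25 this is 1.073 per year, or 107.3 per 100 subject-years. On tofacitinib it is 0.36 × 107.3 = 38.6.

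**3. Any-TEAE hazard ratio.** Let L be the placebo rate of a first non-flare event per 100 subject-years and h the true non-flare hazard ratio, with flares and other events independent. Then

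HR(any) = (h × L + 38.6) / (L + 107.3).

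This is an average of 0.36 and h, weighted by the share of placebo first events that are flares. For L = 100 and h = 1 it is 138.6 / 207.3 = 0.67.

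| L per 100 subject-years | h = 1.0 | h = 1.5 |
|---|---|---|
| 50 | 0.56 | 0.72 |
| 100 | 0.67 | 0.91 |
| 150 | 0.73 | 1.02 |
| 300 | 0.83 | 1.20 |

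Stated instead as a placebo median time to a non-flare TEAE of 28, 60, 120, 236 or 472 days, the result is 0.93, 0.87, 0.78, 0.68 or 0.57 for h = 1.0, and 1.38, 1.27, 1.12, 0.93 or 0.74 for h = 1.5. The more frequent ordinary adverse events are, the weaker the pull.

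**4. If only some planning-rate flares are recorded as adverse events.** Taking half in each arm as an illustration, with L = 100 and h = 1: (100 + 19.3) / (100 + 53.6) = 0.78, instead of 0.67.

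**5. SAE hazard ratio.** Only serious flares enter, so both flare rates are multiplied by the serious share s. With 10 non-flare SAEs per 100 subject-years, s = 10% and h = 1: (10 + 3.86) / (10 + 10.73) = 0.67.

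| s | h = 1.0 | h = 1.5 |
|---|---|---|
| 0% | 1.00 | 1.50 |
| 5% | 0.78 | 1.10 |
| 10% | 0.67 | 0.91 |
| 20% | 0.56 | 0.72 |

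At s = 10% and h = 1, changing the non-flare SAE rate to 5 or 20 per 100 subject-years gives 0.56 or 0.78.

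**6. Check and effect of the fix.** A large simulated Cox analysis (100,000 per arm, non-flare events counted until 28 days after flare) gave these results:

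| Median to non-flare TEAE, days | h | Flares included | Flares excluded |
|---|---|---|---|
| 60 | 1.0 | 0.87 | 0.99 |
| 120 | 1.0 | 0.79 | 1.00 |
| 236 | 1.0 | 0.68 | 1.00 |
| 120 | 1.5 | 1.11 | 1.50 |

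The simulation assumes, as step 3 does, that flares and other events are independent.

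**The case against.** The strongest reply is that these are descriptive outputs. No test, alpha or decision rule depends on them. SAP 6.6.1 also gives separate hazard ratios for adjudicated MAS, serious and opportunistic infections, malignancies, GI perforations and cardiovascular events, and SAP 6.6 summarises cytopenias and laboratory abnormalities. None of these counts flares as such. That stands, and it confines the point to the two pooled measures. General tables follow sponsor standards that are not in the documents and may well show flare as its own term. That would help a reader, but it cannot repair a time-to-first-event hazard ratio in which the flare has already been counted as the event.

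Four stronger readings are tempting, and the documents do not support them.

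- **That tofacitinib is bound to look safer than it is.** The direction depends on tofacitinib preventing flares and on the non-flare hazard ratio being above the flare hazard ratio. The size depends on a non-flare rate that neither document gives.
- **That the safety result simply repeats the primary endpoint.** Under SAP 2.3.1, stopping investigational product for most other reasons counts as a flare. Such stops need not be flare adverse events, so the overlap is partial and 107 per 100 subject-years is an upper-end flare-event rate.
- **That SAE is affected as much as any TEAE.** If no flare is serious, the SAE hazard ratio is untouched.
- **That the sponsor's earlier withdrawal trial already showed the masking.** Protocol 2.3.2 does say of that trial: "A larger proportion of subjects in the placebo group had TEAEs related to the underlying JIA disease than subjects in the tofacitinib 5 mg BID". It also reports similar overall TEAE and SAE proportions between arms. Those proportions are not exposure-adjusted, so they neither show nor exclude masking.

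A reader might also want the summary of adverse events leading to discontinuation changed. SAP 6.6.1 specifies no such summary. Appendix 3.12 records flare stops under insufficient clinical response, and SAP 6.5 tabulates reasons for discontinuation.

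**Conclusion.** The point holds for the any-TEAE incidence rate and hazard ratio, and for the SAE versions to the extent that flares meet a seriousness criterion. As written, these measures cannot be read as drug safety alone.

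Under the design's flare hazard ratio, the pooled ratio is pulled toward 0.36. A true non-flare hazard ratio of 1.0 would appear as about 0.56 to 0.83, and one of 1.5 as about 0.72 to 1.20. This rests on exponential and independent event times, on every planning-rate flare being recorded as an adverse event, and on an assumed first non-flare rate of 0.5 to 3 per placebo subject-year. Fewer recorded flares or commoner ordinary events would bring the ratio closer to the truth. The omission is certain from the text; its size in this trial is not. The primary efficacy analysis and the event-specific safety hazard ratios are not in question.

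**What to change.** In SAP 6.6.1, add double-blind incidence rates and Cox hazard ratios for any TEAE and for SAE that exclude sJIA flare and disease-worsening preferred terms. Fix the term list before unblinding. Subjects with no non-flare event in the risk period are censored at its end, as the section already does for subjects without an event. Report these results beside the all-inclusive ones, which stay.

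The cost is some SAP wording, a term list and one extra set of tables; no new data are needed. There are two downsides. The flare-excluded analyses have fewer events and wider intervals. Flare also still ends follow-up sooner on placebo, and any time counted after it is off assigned treatment, so the text beside the tables should say that follow-up for other adverse events is cut short more often in that arm.

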## 6.7. Additional Analyses Depicting COVID-19 Pandemic Impact

As this study just randomized a few subjects with short follow up time in the double-blind phase before the COVID-19 pandemic anchor date (09 January 2020 for China sites, and 11 March 2020 for the remaining countries) and majority subjects are enrolled during the pandemic, the impact of COVID-19 pandemic is limited. Thus, no additional efficacy analysis will be done.

In order to report the impact of COVID-19 on clinical trial populations and study data, the following additional listings and summaries will be produced for both open-label and double-blind phases, unless noted otherwise:

- A separate summary table solely for subject discontinuations from investigational product and withdrawal from study related to COVID-19 pandemic, if any, will be provided

- Protocol deviations related to COVID-19 pandemic will be summarized and listed separately. Both important and non-important PDs related to COVID-19 pandemic will be reported
- COVID-19 related AEs, if any, will be reported separately.

## 7. INTERIM ANALYSES

The planned analysis is as described in [Section 5.1](#). This analysis will be performed after 28 subjects have reported flare in the double-blind phase. The First Analysis will be completed by the independent SDAC, and the results will be reviewed by the DSMB. More details of the decision criteria, dissemination plan and method of maintaining the study blind will be provided in a separate First Analysis SAP and the DSMB charter.

Unplanned interim analyses (blinded) may be performed to support regulatory submissions in other indications.

### 7.1. Centralized Coordinating Center (CCC)

This study will utilize a CCC to review and confirm, in real time, efficacy assessments, including sJIA fever assessment, JIA core set variables, extra-articular sJIA features, Adapted JIA ACR response, sJIA disease flare and inactive disease, according to validated criteria, at various time points throughout the study.

In addition, the CCC will review corticosteroid (CS) regimens of study participants. The CCC will suggest a customized 4-week CS tapering schedule for each subject entering Part 2. Subjects are required to contact the investigator if they experience any symptoms of a sJIA flare; if required, an extra unscheduled visit will be conducted to assess the adverse event. The tapering schedule will be re-evaluated in consultation with the CCC.

The CCC will also provide recommendations in case participants are not able to maintain a stable CS dose in the double-blind phase. Furthermore, the CCC will provide guidance regarding discontinuation of any subject based on CS regimen.

For data analysis Pfizer will calculate all the efficacy endpoints in-house, except for double-blind flare, which will be obtained from the CCC's real-time assessments mentioned above.

### 7.2. Data Safety Monitoring Board (DSMB)

An independent Data Safety Monitoring Board (DSMB), a group of experts external to Pfizer, will review accumulating safety data from this study on an ongoing basis within the context of the Phase 3 pediatric program as well as adult program. Based on these reviews, the DSMB will have the capacity to make recommendations to Pfizer that might impact the future conduct of the trial. The recommendations made by the DSMB to alter the conduct of the study will be forwarded to Pfizer for final decision. Pfizer will forward such decisions, which may include summaries of aggregate analyses of endpoint events and of safety data which are not endpoints, to regulatory authorities, as appropriate. The DSMB will have access to unblinded treatment information from concurrently ongoing double-blind studies

during the clinical trial. The management and process of this committee will be in accordance with Pfizer's Standard Operating Procedures and will be documented in the DSMB Charter. The DSMB members will all be individuals who are independent of Pfizer. A DSMB Liaison will be appointed; this is an individual who represents Pfizer to coordinate communications and facilitates access to Pfizer's resources, but is not involved in the study design, study management, site management, data accrual, or study analysis. Records of DSMB meetings, interactions with Pfizer contacts, assessments and recommendations and materials reviewed will be maintained and kept proprietary and confidential by the DSMB.

In addition, the DSMB will also evaluate efficacy data at the First Analysis and make a recommendation regarding study continuation based on observed results of the study. The recommendations made by the DSMB will be forwarded to the Sponsor for final decision. The independent Statistical Data Analysis Center (SDAC) will prepare data for DSMB review. Clinical sites and sponsor study team will be restricted from access to study results until the conclusion of the study.

Further information about the DSMB can be found in the DSMB Charter, which outlines the operating procedures of the committee, including specific description of the scope of their responsibilities, including a plan where communication timelines are defined.

### **7.3. Steering Committee**

The Sponsor will use a Steering Committee to provide guidance regarding evaluation of the 5 mg BID dose level of tofacitinib in the initial cohorts of this study. In the open-label phase the Steering Committee will assess preliminary efficacy and safety of the 5 mg BID dose level based on a review of 2 cohorts, each receiving tofacitinib 5 mg BID. The Steering Committee will provide recommendations regarding further enrollment at the 5 mg BID dose level.

Additional details will be provided in a separate Steering Committee Charter.

### **7.4. Safety Endpoint Adjudication Committee**

To help assess specific safety events in this and other studies in the tofacitinib program, adjudication committees have been established to harmonize and standardize selected safety event assessment. Members of these safety event adjudication committees will be blinded to treatment assignment in order to allow for unbiased assessments. These committees include a Cardiovascular Endpoint Adjudication Committee (CV EAC), Malignancy Adjudication Committee (MAC), Opportunistic Infection Review Committee (OIRC), Hepatic Event Review Committee (HERC) and Gastrointestinal Perforation Review Committee (GIPRC), and Macrophage Activation Syndrome (MAS) Review Committee.

Further information about these committees can be found in the respective charters, including specific descriptions of the scope of their responsibilities and the processes and definitions used to review and assess specific safety events.

In addition to these external committees, an internal committee of medically qualified Pfizer personnel with expertise in the assessment and diagnosis of respiratory disease will review

and categorize potential events of interstitial lung disease (Interstitial Lung Disease Committee, ILDRC).

Additional safety event adjudication or review committees may be established to harmonize and standardize selected safety event assessments. As described above, individual committee charters will provide specific descriptions of the scope of responsibilities and the processes and definitions used to review and assess specific safety events.

In addition to the event adjudication or review committees described above, all biopsies of potentially malignant tumors, suspicious lymphadenopathy, or possible extranodal lymphoproliferative disorder should be submitted to the central laboratory for review by central laboratory pathologists. In some instances, additional expert pathology review of submitted samples may be performed. Description of the scope of review and the processes used to obtain and assess biopsies is described in the Histopathology Review for Potential Malignancy charter.

